9.3 Follow-Up Activities

Follow-Up activities are as follows:

- At Day 180 post-baseline, all patients will be administered a repeat dose of AZD7442 600 mg IM or IV. The window for this treatment will be +/- 5 days from the actual due date. The dose will be administered in the same manner as the baseline dose unless patient circumstances require a different route of administration. All requirements listed above for baseline AZD7442 administration both IV and IM will be followed for the repeat dose including the one-hour post-dose observation period.
- Patients will complete follow-up Patient Experience/COA surveys on days 2, 30, 60, 90, 120, 150, 180, 181, 210, 240, 270, 300, 330 and 360 post-baseline at home. The window for these surveys will be +/- 5 days from the actual survey due date except for day 2 survey which is +5 days only.
*NB - Study participants will complete all surveys via mobile phone, desktop, laptop, tablet computer or via Call Center. The study site is not responsible for patient completion of the surveys.
- Patients will complete QoL assessments on days 2, 30, 90, 180, 270, and 360 post-baseline at home. The window for these assessments will be +/- 5 days from the actual due date except for day 2 assessment which is + 5 days only.
- Site personnel will obtain blood for serum concentration of AZD7442 at days 30, 90, 180, 270 and 360 post-baseline in the office for all patients. The window for these blood draws will be +/- 5 days from the actual due date. All

serum concentration measurements will be sent to PPD Bioanalytical Laboratory in Richmond, VA for analysis.

- Site personnel will obtain blood for RBD-IgG antibody level at days 90, 180, 270 and 360 post-baseline in the office for all patients. The window for these blood draws will be +/- 5 days from the actual due date. All RBD-IgG antibody levels will be sent to LabCorp for analysis.
- Site personnel will obtain blood for T-cell assay at Day 30 post-baseline in the office for all patients and send to Isoplexis in Branford, CT for analysis. A subset of patients will be selected including 120 patients with hematologic malignancy and 60 patients with solid tumors in order to have site personnel obtain blood for repeat T-cell assay at Day 210 post-baseline in the office and send to Isoplexis in Branford, CT for analysis. The window for these blood draws will be +/- 5 days from the actual due date.

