- An unsolicited adverse event is an adverse event that is communicated by a participant who has signed the informed consent. Unsolicited AEs include serious and non-serious AEs. Potential unsolicited AEs may be medically attended (i.e., symptoms or illnesses requiring a hospitalization, or emergency room visit, or visit to/by a health care provider). The participants will be instructed to contact the site as soon as possible to report medically attended event(s), as well as any events that, though not medically attended, are of participant concern. Detailed information about reported unsolicited AEs will be collected by qualified site personnel and documented in the participant's records. Unsolicited AEs that are not medically attended nor perceived as a concern by participant will be collected following completion of the follow-up Patient Experience/COA survey by the participant and review of available medical records.
- Solicited AEs are predefined such as injection site reactions and systemic events for which the participant is specifically questioned in the follow-up Patient Experience/COA survey.

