25.8 Recording and Reporting Adverse Events

- For the purpose of processing and reporting adverse events, the study period is defined as that time period from signature of the informed consent form through the last visit of the study. AEs may be reported by the study participant (or, when appropriate, by a caregiver, surrogate, or the participant's legally authorized representative), the PI or the Study Coordinator.
- Reporting of non-serious adverse events will be limited to **ONLY** the following:
 - Any event reported by the patient on his/her follow-up survey in the first 24 hours post-administration of AZD7442
 - Any event reported by the patient on his/her follow-up survey that includes an unplanned telehealth visit, unscheduled physician office visit, ER/Urgent Care Visit
 - Any positive SARS-CoV-2 test by RT-PCR reported to the study site
 - Any symptoms of SARS-CoV-2 reported by the patient on any follow-up survey
 - If the Investigator considers that there was a causal relationship between treatment with AZD7442 or protocol design/procedures and a patient's underlying disease progression, then this must be reported as an AE or SAE.
- All AEs will be collected from baseline AZD7442 administration through day 360 post-baseline. SAEs will be collected from dose administration through the day 360 follow-up visit at the time points specified in the Schedule of Activities. However, any SAEs assessed as related to study participation (e.g., study intervention, protocol-mandated procedure, invasive tests or change in existing therapy) will be recorded from the time participant consents to participate in the study.
- Medical occurrences that begin before the start of study intervention but after obtaining Informed Consent will be recorded as Medical History/Current Medical Conditions not as AEs.
- All SAEs will be recorded and reported to the Sponsor or designee immediately and under no circumstance should this exceed 24 hours. The Investigator will submit any updated SAE data to the Sponsor or designee within 24 hours of it being available.
- Investigators are not obligated to actively seek information on AEs or SAEs after the conclusion of study participation. However, if the investigator learns of any SAE, including a death, at any time after a participant has been discharged from the study, and he/she

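### The Day 181 survey is timed from baseline with a ±5-day window, not from the second AZD7442 dose, so a compliant patient can complete it before that dose

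*Protocol*

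**What the plan says.** Section 9.3 of the protocol fixes the second dose and the surveys independently of each other.

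- **Second dose.** Every patient is due a second dose at Day 180, counted from baseline, and the margin is stated separately: "The window for this treatment will be +/- 5 days from the actual due date".
- **Surveys.** There are 14 follow-up surveys, done at home on day numbers counted from baseline, with Days 180 and 181 both on the list. Their margin reads: "The window for these surveys will be +/- 5 days from the actual survey due date except for day 2 survey". That one exception may run up to five days late but never early.
- **Schedule of Activities.** It repeats ±5 under Day 181 and +5 under Day 2. The survey is the only activity marked in the Day 181 column.

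Section 9.3 carries the baseline administration requirements and the one-hour observation over to the second dose. It carries over no rule on survey timing. It also says that sites are not responsible for whether patients complete the surveys.

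On adverse events, section 18.2 restricts non-serious event collection to specified follow-up survey answers, one of which concerns the 24 hours after administration. Section 25.8 gives a similar closed list, which includes "Any event reported by the patient on his/her follow-up survey in the first 24 hours post-administration of AZD7442". Section 25.7.1 likewise makes the follow-up survey the place where patients are asked about predefined local and systemic reactions.

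**The concern.** AZD7442 is given on Day 1 and at Day 180, and Days 2 and 181 are the only surveys placed one day after a nominal dose. The evident purpose of both is to ask about reactions soon after dosing. For the first dose the timing works, because the Day 2 survey cannot be completed early. For the second dose nothing prevents early completion, and nothing links the survey to the day on which the dose was given.

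A survey completed before the dose cannot report a reaction to it. A survey completed on the day of the dose cannot cover the full 24 hours. What is at stake is the record of non-serious second-dose reactions. It feeds the secondary endpoints in section 14.1 on AZD7442-related side effects (solid tumor versus hematologic malignancy) and on adverse event rates across the four treatment strata. Repeat dosing every six months is the regimen under study, so tolerability of the second dose matters.

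**Working it through.** The protocol states no figure to reproduce here. The check is a count of the day combinations that it permits.

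**Inputs, all from section 9.3 and the Schedule of Activities**
- Second dose, day d: 180 ±5, so 175 to 185 (11 days).
- Day 181 survey, day s: 181 ±5, so 176 to 186 (11 days).
- Day 180 survey: 180 ±5, so 175 to 185 (11 days).
- Day 210 survey: 210 ±5, so 205 to 215.
- Day 2 survey: Days 2 to 7, always after the Day 1 dose.

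**Day 181 survey against the second dose** (11 × 11 = 121 pairs)
- Survey before dose: for each d the number of earlier survey days is 0, 0, 1, 2, …, 9. The sum is 45, and 45/121 = 37.2%.
- Survey on the dose day: the windows share Days 176 to 185, giving 10 pairs (8.3%).
- Survey on the day after the dose: 11 pairs. Later than that: 55 pairs. Check: 45 + 10 + 11 + 55 = 121.
- The survey can fall from 9 days before the dose (176 − 185) to 11 days after it (186 − 175).

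**Two special cases**
- Dose exactly on Day 180: survey Days 176 to 179 are in window and precede the dose (4 of 11 days).
- Both surveys exactly on their due dates: doses on Days 182 to 185 (4 of 11 days) come after both.

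**Is the Day 180 survey a backup?**
- Alone, it precedes the dose in 0 + 1 + … + 10 = 55 of 121 pairs.
- Both surveys precede the dose in Σ k(k − 1) combinations, where k = d − 175 runs from 1 to 10. That is 385 − 55 = 330 of 11 × 11 × 11 = 1,331, or 24.8%.

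**Next survey**
- Day 210 falls between 205 − 185 = 20 and 215 − 175 = 40 days after the dose.

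**Two possible corrections**
- Still counted from baseline, but +5 only (Days 181 to 186): 11 × 6 = 66 pairs. The survey precedes doses on Days 182 to 185 in 1 + 2 + 3 + 4 = 10 of them (15.2%), and 5 more fall on the dose day.
- Counted from the actual dose, due at d + 1, +5 only: again 66 pairs, with 0 on or before the dose. The survey falls 1 to 6 days after it.

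**The case against.** The windows are not in dispute. The case on the other side is that larger claims could be built on them than the protocol supports, and most of it stands.

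- **Day 181 as the only survey that can capture 24-hour reactions.** A reader might infer this, but the protocol does not say which questions each survey asks. Day 180 can follow an early dose, and Day 210 could ask about the first 24 hours with long recall. The supportable statement is that Day 181 is the only survey scheduled for the day after the nominal second dose.
- **Second-dose reactions systematically lost.** Other routes exist. The one-hour observation applies to the second dose. Section 25.7.1 tells participants to contact the site about medically attended events and about others that concern them, and provides for review of medical records. Serious events are reported by the site. Sections 18.2 and 25.8 narrow non-serious reporting largely to survey answers and so sit uneasily with 25.7.1, but the routes are there.
- **The second dose made to look better tolerated than the first.** No dose-to-dose comparison is a listed endpoint. Capture after the first dose is not assured either, because the Day 2 survey can be skipped.
- **Bias between groups.** Equal loss in every group lowers the rates without favoring any group. Bias needs dose or survey timing to differ by group, and the protocol gives no information on that.
- **A number of patients affected.** Applying 37% to all 1,500 gives roughly 550. That assumes uniform, independent timing and that every patient is retained, redosed and surveyed. The protocol supports none of this.

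None of these points removes the timing defect.

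**Conclusion.** The point holds as a data-collection defect that should be fixed. A fully compliant patient can complete the Day 181 survey before the second dose in 45 of 121 permitted day pairs, and on the dose day in 10 more. Both nearby surveys precede the dose in 330 of 1,331 combinations. These are counts of permitted combinations and not probabilities. How often it would happen depends on when patients are redosed and when they answer, which the protocol does not tell us.

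The exposed data are non-serious, unattended reactions to the second dose that arise after the first hour. Missing them, or collecting them 20 to 40 days later, would understate AZD7442-related side-effect rates. Comparisons between groups are biased only if timing differs by group. The primary endpoint (serum concentration) and the infection endpoints do not depend on this survey.

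**What to change.** In sections 5.5 and 9.3 and in the Schedule of Activities, define the Day 181 survey as due one day after the actual date of the second dose, with a window of +5 days only. This mirrors the Day 2 survey. The data platform should release it when the site records the second dose.

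Changing the window to +5 only while still counting from baseline is not enough, as the 10 remaining pairs show. The dose, its schedule and the Day 180 survey need no change.

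The cost is a sentence in each section, a schedule footnote and a changed survey trigger, with no extra visit or survey. The downside is that the platform must receive the date of the second dose promptly from the site. The change helps only patients not yet redosed, so it is best made before second doses begin.

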11.1 COVID-19 assessment

In the current study, clinical severity of SARS-CoV-2 disease will be assessed throughout a patient’s participation in the study in accordance with the 9-point World Health Organization (WHO) Ordinal Scale (WOS) consisting of the following categories:

**11.0
WHO
Ordinal
Scale**

WOS	Clinical Severity	Criteria
0	Uninfected	No evidence of infection
1	Mild	No limitation of activities
2	Mild	Limitation of activities
3	Moderate	Hospitalized, no oxygen therapy

4	Moderate	Hospitalized, oxygen by mask or nasal prongs
5	Severe	Hospitalized, non-invasive ventilation or high-flow oxygen
6	Severe	Hospitalized, invasive ventilation without other organ support (e.g., ECMO, CRRT, vasopressors)
7	Severe	Hospitalized, ventilation + additional organ support (e.g., ECMO, CRRT, vasopressors)
8	Dead	Death

Source: World Health Organization, 2020

**12.0
Program
Products**

12.1 Program Product Dosage and Administration

- AZD7442 600 mg (6.0 ml) dose for all participants will be provided by AstraZeneca and distributed to all sites from a central location.
- AZD7442 will be administered by all AISP participating locations according to protocol guidelines.
- AZD7442 600 mg IM will be administered according to FDA approved guidelines for administration.
- AZD7442 600 mg IV will be administered only according to the instructions in Section 9.2 of this protocol.

12.2 Other Medications

Participants will continue administration and dose scheduling of all other medications as prescribed and in accordance with their normal medical practice

**13.0
Primary
Endpoint**

13.1 Primary Endpoint

The study's primary endpoint will assess AZD7442 serum concentration collected on days 30, 90, 180, 270, and 360 post-baseline in all patients.

13.2 Primary Endpoint Assessment

AZD7442 serum concentrations at 30, 90, 180, 270 and 360-days post-baseline will be assessed using a mixed model for repeated measures. The primary endpoint will be analyzed for the Intent-To-Treat (ITT) and Per-Protocol (PP) populations.

**14.0
Secondary
And Exploratory
Endpoints:
Overall Study**

14.1 Definitions and Secondary Endpoints

Definition of SARS-CoV-2 qualifying symptoms:

SARS-CoV-2 qualifying symptoms are based on the definitions in the AstraZeneca PROVENT trial. In combination with a positive SARS-CoV-2 antigen test, symptomatic infection includes at least one of the following symptoms and duration:

- No minimum duration
 - Fever, shortness of breath, difficulty breathing, new onset confusion (only for patients ≥ 60 years), appetite loss or decrease food intake (only for patients ≥ 60 years), increased supplemental oxygen requirement (only for patients ≥ 60 years on baseline supplemental oxygen)
- Must be present for ≥ 2 days
 - Chills, cough, fatigue, muscle aches, body aches, headache, new loss of taste, new loss of smell, sore throat, congestion, runny nose, nausea, vomiting, diarrhea

Secondary Endpoints will include the following:

- Incidence of symptomatic SARS-CoV-2 infections including but not limited to those with SARS-CoV-2 related hospitalization and/or SARS-CoV-2 related death compared between solid tumor and hematologic malignancy patients.
- Incidence of symptomatic SARS-CoV-2 infection including but not limited to SARS-CoV-2 related hospitalization and/or SARS-CoV-2 related death compared between patients treated with chemotherapy only, immunotherapy only, targeted therapy only or other/combination therapy only over 12 months post-baseline.
- Serum AZD7442 concentrations at 1, 3, 6, 9 and 12-months post-baseline compared between solid tumor and hematologic malignancy patients.
- Serum AZD7442 concentrations at 1, 3, 6, 9 and 12-months post-baseline compared between patients treated with chemotherapy only, immunotherapy only, targeted therapy only or other/combination therapy only.

- Correlation of the incidence of symptomatic SARS-CoV-2 infection including but not limited to those with SARS-CoV-2 related hospitalization and/or SARS-CoV-2 related death to the levels of serum concentration of AZD7442 at 1, 3, 6, 9 and 12-months post-baseline in all patients.
- Incidence of symptomatic SARS-CoV-2 infection including but not limited to SARS-CoV-2 related hospitalization and/or SARS-CoV-2 related death compared between patients currently on active treatment, ≤ 3 months post-treatment and > 3 months and ≤ 12 months post-treatment regardless of treatment strata.
- Incidence of Severe SARS-CoV-2 (pneumonia or hypoxemia) and WHO score of ≥ 5 compared between all four strata
- Time to first event (e.g., SARS-COV-2 RNA by RT-PCR positivity, symptomatic SARS-CoV-2 infection, hospitalization, death) post-treatment compared between all four strata
- Quality-of-Life metrics in all cancer patients, as measured by change from baseline to days 30, 90, 180, 270 and 360 post-baseline, compared between each of the four strata
- Patient symptom safety and rate of adverse events including medically attended visits, ER/urgent care/unplanned telehealth visits using Patient Experience/COA survey data summarized and compared in each of the four strata
- Incidence of AZD7442-related side effects compared between solid tumor and hematologic malignancy disease cohorts
- Predict the incidence of SARS-CoV-2 infection based on serum concentration of AZD7442 at days 30, 90, 180, 270 and 360 post-baseline in all cancer patients using machine learning algorithms.

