5.6 Study Data

Study data for all qualified patients will be collected and stored on a proprietary data platform that has been tested and validated by a HIPAA compliant review system. This platform provides for role-based accountability. The platform is called the National Medication Safety, Outcomes and Adherence Platform (NMSOAP). The data collection for all study participants that receive AZD7442 treatment will include: one baseline Experience/COA survey, one baseline QoL assessment, 14 follow-up Experience/COA surveys, 5 follow-up QoL assessments, at least 5 serum concentrations of AZD7442, at least 5 SARS-CoV-2 RBD-IgG antibody levels, and at least 2 CD4/CD8 measurements. An additional AZD7442 serum concentration, SARS-CoV-2 RBD-IgG antibody level and CD4/CD8 assay will be performed if a symptomatic patient becomes SARS-CoV-2 RNA by RT-PCR COVID-19 positive. In this case, additional medical records will be obtained. These could include unplanned telehealth visit, Urgent Care/ER visit or hospitalization, pharmacy data and medical insurance claims data.

6.0 Sites, Subjects Stratification
	
6.1 Sites The study will be conducted at up to 75 hematology/oncology medical practice locations nationally.
 
6.2 Subjects The program will enroll approximately 1,500 qualified patients divided into approximately 1,200 qualified solid tumor and approximately 300 qualified hematologic malignancy patients either on active therapy or treated within the past 12 months.
 
6.3 Stratification Qualified solid tumor and hematologic malignancy patients will be stratified based on current or former treatment with chemotherapy only, immunotherapy only, targeted therapy only, or other therapy/combination therapy only and sub-stratified by: currently on active treatment, ≤3 months post-treatment or >3 months and ≤12 months post-treatment.

7.0 Study Duration
	
 ➤ Enrollment: Approximately 3 months ➤ Patient Follow-Up: 12 months from date of enrollment

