- In the event that a patient develops any symptoms that could be possibly related to SARS-CoV-2 infection at home or out of the office, the patient must immediately test themselves using the SARS-CoV-2 Home Test Kit that was given to them at enrollment or go to a facility that can perform an EUA approved Breath Test for SARS-CoV-2 infection.
- In the event a positive test from the SARS-CoV-2 Home Test Kit or EUA approved Breath Test for SARS-CoV-2 infection is recorded, the patient must go to a qualified testing center and receive a SARS-COV-2 RNA by RT-PCR nasal swab test. These include LabCorp or Quest Diagnostics or a location that uses one of these two labs for the analysis (e.g., CVS).
- A positive SARS-COV-2 RNA by RT-PCR test must be sent to a qualified genomics laboratory (LabCorp or Quest Diagnostics) for detailed virus analysis
- In the event that a patient tests positive for SARS-CoV-2 infection by SARS-COV-2 RNA by RT-PCR, the patient should be instructed to contact their oncology center immediately
- In the event that a patient tests positive for SARS COV-2 RNA by RT-PCR, the patient must have blood drawn for serum concentration of AZD7442, RBD-IgG antibody level and T-cell analysis in the office approximately 10

days after the patient reported a positive test or in whatever timeframe is the acceptable protocol for a positive patient returning safely to the office of the Investigator.

- In the event that a patient develops a SARS-CoV-2 infection with symptoms, the patient should be immediately treated in accordance with Investigator judgement. Such treatment should include the current standard of care for symptomatic SARS-CoV-2 positive infection depending upon availability of immediate treatment. Such patient will be followed until day 360 of the study with all study procedures and assessments.
- Automatic request for patient medical records, pharmacy fill/refill data and medical insurance claims data for all patients for the 12 months post-baseline will be sent and forwarded to MediMergent for analysis.

[figure not shown]
Schedule of Activities:

	Screening/ Day 1 Baseline	Day 2	Day 30	Day 60	Day 90	Day 120	Day 150	Day 180	Day 181	Day 210	Day 240	Day 270	Day 300	Day 330	Day 360
Visit Window (Days)		+5	± 5	± 5	± 5	± 5	± 5	± 5	± 5	± 5	± 5	± 5	± 5	± 5	± 5
Informed Consent	X														
Authorization for Release of Health Info	X														
Inclusion/ Exclusion	X														
CBC including Platelet Count (if necessary)	X														

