- AZD7442 (Evusheld) has demonstrated reduced neutralization activity against the Omicron BA.1 variant (which is B.1.1.529), with a 132- to 183-fold reduction in neutralization activity seen in pseudotyped virus-like particle (VLP) assays and a 12- to 30-fold reduction in neutralization activity seen in authentic virus assays. Likewise, AZD7442 (Evusheld) demonstrated reduced neutralization activity against the Omicron BA.1.1 variant (which comprised 57% of circulating variants in the United States in the week ending 3/19/22 per <https://covid.cdc.gov/covid-data-tracker/#variant-proportions>), with a 424-fold reduction in neutralization activity seen in VLP assays and a 176-fold reduction in neutralization activity seen in authentic virus assays. Neutralization activity of AZD7442 (Evusheld) against the Omicron BA.2 variant is minimally impacted.
- Of the Omicron binding site substitutions relevant to AZD7442 that have been tested to date in preclinical assays, none have been associated with escape from AZD7442 neutralization. In vitro findings demonstrate that AZD7442 neutralizes other emergent SARS-CoV-2 viral variants, including the Delta and Mu variants.
- As of June 28, 2022 the EUA for AZD7442 has been modified and the dosing interval for AZD7442 has been adjusted to a repeat dosing of 600 mg IM or IV 6 months after the initial dose.

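### The concentration–infection analyses use raw AZD7442 level with no calendar or variant term, although the protocol itself reports potency losses from minimal to 424-fold between variants

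*Protocol*

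**What the plan says.** **Endpoint.** Protocol 3.2 and 14.1 relate symptomatic infection, with related hospitalization and "SARS-CoV-2 related death to the levels of serum concentration of AZD7442 at 1, 3, 6, 9 and 12-months post-baseline in all patients". Section 3.2 repeats the objective for severe disease. The machine-learning endpoint in 14.1, taken up in 22.1, is to "Predict the incidence of SARS-CoV-2 infection based on serum concentration of AZD7442 at days 30, 90, 180, 270 and 360 post-baseline".

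**Adjustment.** For secondary comparisons, 17.6 foresees logistic or linear mixed models that account for patient and disease factors where appropriate. Neither calendar time nor variant is named there or elsewhere in section 17.

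**Potency by variant (23.5).** BA.1.1 comes "with a 424-fold reduction in neutralization activity seen in VLP assays and a 176-fold reduction in neutralization activity seen in authentic virus assays". For BA.1 the loss is put at 132- to 183-fold in virus-like particles, against only a "12- to 30-fold reduction in neutralization activity seen in authentic virus assays". For BA.2: "Neutralization activity of AZD7442 (Evusheld) against the Omicron BA.2 variant is minimally impacted". Section 23.5 also says that the authorised dose was raised from 300 mg to 600 mg because of BA.1 and BA.1.1, and it gives a dated variant share (BA.1.1 at 57% in one week of March 2022).

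**Timing and design.** Section 7.0 gives "Enrollment: Approximately 3 months" and 12 months of follow-up. All patients are dosed at baseline and Day 180 (9.3), and all receive active drug (5.1).

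**Variant data.** A positive RT-PCR sample "must be sent to a qualified genomics laboratory" (9.3). The stated uses are exploratory surveillance (14.3) and a descriptive profile of breakthrough cases (17.10).

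**The concern.** A concentration–infection analysis is useful only if a given level means roughly the same protection throughout the data. The protocol's own background section says that this depends on the variant.

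Patients enter within about 3 months and follow the same dosing days, so level, time since dose and calendar date are linked. Calendar date brings both the circulating variant and the general infection pressure, and no untreated arm shows the background epidemic. A wave that falls in a low-level stretch can make concentration look more protective than it is. A wave in a high-level stretch can hide a real effect. Mixing sensitive and resistant variants flattens the slope.

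At stake is any protective level read from these secondary analyses. The primary endpoint is serum concentration itself and is not affected.

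**Working it through.** The protocol states no event count, power or expected slope for this endpoint, so there is no figure to reproduce. The checks below show the mechanism; they do not measure bias in this trial.

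**1. What one level could mean under different variants.** Assume protection = C / (C + fold × EC50), with fold = 1 for a sensitive variant.

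| Fold loss (23.5) | C = 100 × EC50 | C = 10 × EC50 |
|---|---|---|
| 1 (BA.2, minimal) | 100/101 = 99% | 10/11 = 91% |
| 12 (BA.1, authentic, low) | 100/112 = 89% | 10/22 = 45% |
| 30 (BA.1, authentic, high) | 100/130 = 77% | 10/40 = 25% |
| 176 (BA.1.1, authentic) | 100/276 = 36% | 10/186 = 5% |
| 424 (BA.1.1, VLP) | 100/524 = 19% | 10/434 = 2% |

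**2. How far concentration moves within a dosing interval.** The ratio of Day 30 to Day 180 is 2^(150/half-life). The protocol gives no half-life. Assuming 90, 60 and 45 days, the ratio is 3.2, 5.7 and 10.1.

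**3. Calendar structure.** Accrual of 3 months plus 12 months of follow-up spans about 15 calendar months. At one nominal study day, patients differ by about 3 months in calendar date. Between Day 30 and Day 360 each patient moves 330 days. The calendar link is therefore weak within a timepoint and strong across timepoints. The Day 180 dose breaks it in part: Days 90 and 270 are both about 90 days after a dose, and Days 180 and 360 both about 180 days, in each case about six months apart.

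**4. Infection pressure alone.** Suppose concentration has no effect and infection pressure is k times higher in the low-level stretch. The apparent log-hazard slope on log concentration is -ln k / ln R, where R is the ratio in step 2. For an assumed k = 2, it is -0.693/1.155 = -0.60 at a 90-day half-life and -0.693/2.310 = -0.30 at 45 days. If the higher pressure falls in the high-level stretch, the sign reverses.

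**5. Variant change alone.** Illustrative simulation, all parameters assumed: 1,500 patients, uniform accrual over 90 days, intervals starting at Days 30, 90, 180 and 270, background hazard 5% per month, half-life 60 or 90 days, the protection formula above, one variant change at calendar day 150 or 240, and 20 replicates per setting. The Day 180 trough was carried across the next interval, a simplification. Entries are ranges, over the four settings, of the slope of log-odds of infection per unit of log concentration.

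| Fold loss after change | Pooled | Before change | After change |
|---|---|---|---|
| 1 | -0.79 to -0.91 | -0.88 to -1.20 | -0.69 to -0.85 |
| 12 | -0.54 to -0.68 | -0.84 to -1.08 | -0.19 to -0.32 |
| 30 | -0.47 to -0.61 | -0.91 to -0.98 | -0.09 to -0.18 |
| 176 | -0.40 to -0.54 | -0.84 to -1.03 | -0.01 to -0.02 |
| 424 | -0.40 to -0.52 | -0.87 to -1.06 | -0.01 to 0.01 |

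With a potency loss, the pooled slope lies between the two periods and describes neither. The sign does not change here; this part of the mechanism is dilution.

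**The case against.** The strongest reply is that covariates for one secondary correlation belong in the SAP, which is not at hand. Section 17.6 names its adjusters for group comparisons and only where appropriate, and 17.12 leaves other endpoints to case-by-case choice. This stands in part: the protocol does not forbid calendar adjustment. But it does fix the exposure scale and the patient set, and the only class of adjuster it names omits the factor that its own background section shows to matter.

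Several stronger readings are tempting and are not supported:

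- *The protocol states that variants are pooled.* It does not. The reference to all patients defines the patient set; pooling is inferred from the absence of any variant or calendar term.
- *Each fixed-day correlation is confounded by the calendar.* With about 3 months' accrual, patients at one timepoint share roughly one window. The confounding needs timepoints to be combined, and Day 180 redosing weakens it.
- *The ratio of 176–424 to 3–10 is the size of the bias.* It sets in vitro losses beside concentration ratios from assumed half-lives, and measures no bias.
- *This is the trial's only exposure–response result.* Sections 3.2 (severe disease), 14.3 (levels before the event), 16.1 (change in level and WHO score) and 17.10 contain related analyses.
- *Every infection will be sequenced.* Section 9.3 requires positives to be sent, but 17.10 accepts cases with or without genomics, and 17.5 accepts records or claims.

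Section 23.5 also says that no tested Omicron substitution was associated with escape. That sits uneasily beside its fold losses but does not withdraw them.

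**Conclusion.** The point holds in limited form. An analysis that combines timepoints on raw concentration, without calendar period, mixes the effect of concentration with infection pressure and circulating variant. At a single timepoint the main effect is dilution across variants.

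Direction and size are unknown: the fold losses are in vitro, and the documents do not say which variants circulated during follow-up. A reader might infer that the trial will report a false protective level. The documents show only that the stated analysis could not tell such a result from a true one. The slopes and apparent effects in the working rest on assumed half-lives, hazards and a simple protection curve.

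The matter deserves correction because the remedy is cheap, but it concerns secondary analyses only.

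**What to change.** In 14.1 and 17.6 (or the SAP), specify that the concentration–infection analysis is stratified by, or compared within, calendar period, such as month or dominant-variant period. Use the most recent concentration before infection for cases and the latest available level at the same date for comparators. Do not use the sample taken about 10 days after a positive test as the exposure. Add calendar period to the machine-learning inputs in 22.1.

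The text should also say how two gaps are handled: infections before Day 30 have no earlier level, and between Day 180 and Day 270 the latest level may predate the repeat dose.

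Keep analyses by sequenced variant, or with concentration scaled to variant potency, as sensitivity analyses. Sequencing may be incomplete, and the protocol gives fold changes but no variant-specific neutralizing concentrations.

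The cost is some loss of precision and a little more analysis work. The main change uses dates already collected and needs no new samples, visits or patients.
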